### **15.5 Analysis set**

The safety analysis set include all patients who have received any dose of the rhIL-7-hyFc.

The efficacy analysis set for the randomized phase II portion of the study includes all patients who have received a dose of rhIL-7-hyFc, completes CBC at baseline and at ~4 weeks prior to adjuvant TMZ, and have evaluable ALC measurements from the CBC labs. The primary analyses will focus on the intent to treat (ITT) patients regardless what treatment they actually receive.

The PFS evaluable patients include patients who received at least one dose of rhIL-7-hyFc.

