#### **4.4 Randomization**

A total of 20 patients during phase II will be randomized 1:1 to receive either placebo or rhIL-7hyFc at the dose determined during phase I. Patients will be stratified by concomitant use of steroids (Yes/No). This study is double-blinded (participant, and physician/study coordinator are all blinded; pharmacist and study statistician are not blinded). Approximately equal number of patients will be assigned to each treatment group. The randomization will be performed in OnCore. Randomization will occur on eligible patients only and is auto generated after the eligibility is confirmed, the patient has an on-study date, and the strata steroid use (Yes/No) is confirmed; which will return either an 'A' or 'B' assignment. Only the pharmacist and statistician will know the treatment corresponding to each assignment.

Patients enrolled to the phase II expansion cohort will not be randomized.

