## **5.6      Toxicity, Response, and DLT Evaluations**

All patients who receive any study treatment are evaluable for toxicity. Patients are evaluated from first receiving study treatment until a 30-day follow up after the conclusion of treatment or death.

All patients are evaluable for disease response unless they discontinue treatment prior to having any disease assessment.

A patient is evaluable for DLT assessment only during the first 30 days after the first dose of rhIL-7-hyFc treatment and only if enrolled in phase I of the study.

Only patients enrolled to phase I or the randomized phase II portions of the study are evaluable for the secondary and exploratory objectives.

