### 7.1.3 Reporting to the FDA

The conduct of the study will comply with all FDA safety reporting requirements. **PLEASE NOTE THAT REPORTING REQUIREMENTS FOR THE FDA DIFFER FROM REPORTING REQUIREMENTS FOR HRPO/QASMC.** It is the responsibility of the Washington University Principal investigator to report to the FDA as follows:

- Report any unexpected fatal or life-threatening suspected adverse reaction (refer to Appendix C for definitions) no later than **7 calendar days** after initial receipt of the information.
- Report a suspected adverse reaction that is both serious and unexpected (SUSAR, refer to Appendix C) no later than **15 calendar days** after it is determined that the information qualifies for reporting. Report an adverse event (refer to Appendix C) as a suspected adverse reaction only if there is evidence to suggest a causal relationship between the drug and the adverse event, such as:
  - A single occurrence of an event that is uncommon and known to be strongly associated with drug exposure
  - One or more occurrences of an event that is not commonly associated with drug exposure but is otherwise uncommon in the population exposed to the drug
  - An aggregate analysis of specific events observed in a clinical trial that indicates those events occur more frequently in the drug treatment group than in a concurrent or historical control group
- Report any findings from epidemiological studies, pooled analysis of multiple studies, or clinical studies that suggest a significant risk in humans exposed to the drug no later than **15 calendar days** after it is determined that the information qualifies for reporting
- Report any findings from animal or in vitro testing that suggest significant risk in humans exposed to the drug no later than **15 calendar days** after it is determined that the information qualifies for reporting
- Report any clinically important increase in the rate of a serious suspected adverse reaction of that listed in the protocol or IB within **15 calendar days** after it is determined that the information qualifies for reporting

Submit each report as an IND safety report in a narrative format or on FDA Form 3500A or in an electronic format that FDA can process, review, and archive. Study teams must notify the Siteman Cancer Center Protocol Development team of each

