### **15.3.2 Endpoint**

The primary endpoint of Phase II is the % increase of ALC in evaluable patients prior to adjuvant TMZ (at ~ Week 4) that measures the “pure” drug effect before influences from TMZ in reference to the baseline prior to rhIL-7-hyFc injection. A patient is considered evaluable for the primary endpoint if (s)he completes CBC at baseline and at ~4 weeks after the first dose of NT-17 or placebo and has valid ALC measurements prior to and at ~week 4 before adjuvant TMZ of treatment with NT-17 or placebo. Enrolled patients who are not evaluable for the primary endpoint will be replaced so as to meet the study power requirements (see 15.3.3).

The secondary endpoints include lymphocyte counts over time in the setting of steroid use and chemotherapy, progression free survival (PFS) and overall survival (OS).

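### Section 15.5 defines the safety and randomized phase II efficacy sets by receipt of rhIL-7-hyFc only, does not limit its PFS sentence to the single-arm parts, and names ITT as primary although the week-4 ALC comparison is evaluable-only

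*Combined protocol and SAP*

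**What the plan says.** Section 15.5 contains three set definitions and one statement about the primary analyses.

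- Safety: "The safety analysis set include all patients who have received any dose of the rhIL-7-hyFc".
- Phase II efficacy: "The efficacy analysis set for the randomized phase II portion of the study includes all patients who have received a dose of rhIL-7-hyFc". The sentence goes on to require a baseline CBC, a CBC at about four weeks before adjuvant TMZ, and evaluable ALC values from both.
- PFS: "The PFS evaluable patients include patients who received at least one dose of rhIL-7-hyFc".
- Primary analyses: "The primary analyses will focus on the intent to treat (ITT) patients regardless what treatment they actually receive".

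Other sections treat placebo patients as part of the analysis. Section 4.4 states: "A total of 20 patients during phase II will be randomized 1:1 to receive either placebo or rhIL-7hyFc". Section 15.3.2 states: "The primary endpoint of Phase II is the % increase of ALC in evaluable patients prior to adjuvant TMZ". It defines evaluability by ALC values before and about four weeks after a first dose of either study drug or placebo, and replaces enrolled patients who do not qualify. Section 15.3.5 compares ALC between the two arms by t-test or rank-sum test and compares PFS and OS by log-rank test, on data as observed and with no imputation. Section 15.7 compares the mean ALC increase on study drug with that on placebo. Section 5.6 states: "All patients who receive any study treatment are evaluable for toxicity".

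**The concern.** An analysis-set section decides who is counted. Here the section that should settle the matter conflicts with the sections that describe the analyses.

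For the primary endpoint, the set as worded has one arm and the test needs two. For safety, placebo patients are evaluable for toxicity under 5.6 but belong to no safety set under 15.5. For PFS, the wording suits phase I and the expansion cohort, where everyone receives study drug, but not the randomized comparison in 15.3.5.

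The ITT statement raises a separate problem. A reader told that the primary result is ITT will assume that every randomized patient is in it. Under 15.3.2 and 15.3.5, a patient without a valid week-4 ALC is left out of that comparison and replaced. With 10 patients per arm, and a study statistician who is not blinded (4.4), membership of the primary set should not have to be inferred from other sections.

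**Working it through.** **1. The passages side by side**

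| Set | Rule in 15.5 | Rule or use elsewhere |
|---|---|---|
| Safety | any dose of rhIL-7-hyFc | 5.6: any study treatment |
| Phase II efficacy | a dose of rhIL-7-hyFc, plus baseline and week-4 ALC | 15.3.2: study drug or placebo, plus baseline and week-4 ALC; 15.3.5 and 15.7: compared with placebo |
| PFS | at least one dose of rhIL-7-hyFc, no study part named | 15.3.5: log-rank between randomized arms; 15.4.2: primary endpoint of the single-arm expansion cohort |
| Primary analyses | ITT | 15.3.2: evaluable patients, others replaced; 15.3.5: no imputation |

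No other sentence in 15.5 brings placebo patients in.

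**2. The efficacy set taken literally**

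Sections 4.4 and 15.3.3 give 20 patients, 10 per arm. If every patient receives the assigned treatment, none of the 10 placebo patients has received rhIL-7-hyFc, so the placebo arm of the set has n = 0 and a two-sample test cannot be computed.

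**3. The plan's own figure needs both arms**

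Inputs from 15.3.3: means 1486 and 850, SD 480, one-sided 5% two-sample t-test with equal variance, 8 per arm, 80% power.

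- Difference: 1486 − 850 = 636.
- Noncentrality: 636 / (480 × √(1/8 + 1/8)) = 636 / 240 = 2.65, with 14 degrees of freedom.
- Power from the noncentral t distribution: 80.9%, against 80% stated.

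The figure reproduces, and it rests on 8 evaluable placebo patients. Inflating for 10% dropout gives 8 / 0.9 = 8.9, or 9 per arm; the plan has 10. The sample size is not in question.

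**4. Whether the evaluable set would differ from ITT**

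The comparison uses one post-baseline time point. Without imputation, a randomized patient with no valid value there contributes nothing to it. The two sets coincide only if every randomized patient is evaluable.

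The documents give no non-evaluable rate. As an illustration, take the dropout of about 10% in 15.3.3 as that rate and treat patients as independent:

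- Expected non-evaluable: 20 × 0.10 = 2.0.
- Chance of at least one: 1 − 0.90^20 = 0.878.
- At 5%: 1 − 0.95^20 = 0.642.
- At 20%: 1 − 0.80^20 = 0.988.

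If replacement raises the number randomized above 20, these chances do not change, because a replacement is needed only once someone is non-evaluable.

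**The case against.** The strongest reply is that the intent is clear. Section 15.3.2 gives a specific definition of who is evaluable for the primary endpoint and includes placebo; 15.3.5 and 15.7 compare arms. No analyst would drop the control group because of one sentence in 15.5. That is fair as to intent, and it limits the point to a drafting error. It does not remove the conflict: both rules are in force, and only one of them can be followed.

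On PFS, the sentence fits phase I and the expansion cohort and is not clearly exclusive. That stands. What is missing is a limit to those parts, or a rule for the randomized comparison.

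On ITT, the sentence explains itself by reference to treatment actually received and directly follows the ALC requirement, so it can be read as meaning evaluable patients by assigned arm. That reading is possible and is probably what was meant, but the text does not say so. Section 15.3.5 does not itself use the word evaluable, and its repeated-measures models could use patients with no week-4 value. So the ITT criticism applies to the week-4 comparison, and it concerns the label.

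A reader might also infer that leaving placebo out of the safety set disables the FDA trigger in 7.1.3, which looks at whether "those events occur more frequently in the drug treatment group than in a concurrent or historical control group". The documents do not support this. Toxicity evaluability, AE recording and AE capture are governed by 5.6, section 7 and 11.1, none of which is limited to rhIL-7-hyFc recipients. The 7.1.3 wording is one example of causal evidence and also allows a historical control. In addition, 15.3 lists no between-arm AE analysis for phase II. The supported safety inconsistency is 15.5 against 5.6.

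**Conclusion.** The point holds as an error in the set definitions and should be fixed. As written, the safety and phase II efficacy sets leave out placebo patients, and the PFS sentence is not confined to the parts of the study it fits. Followed literally, the phase II efficacy set cannot support the planned two-sample test. The week-4 ALC comparison is an evaluable-patient analysis by assigned arm and should not be reported as ITT.

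The n = 0 result assumes that all patients receive the assigned treatment. The illustration of about 2 of 20 non-evaluable patients and an 87.8% chance of at least one (64.2% at 5%, 98.8% at 20%) assumes that dropout equals week-4 non-evaluability and that patients are independent. It shows that the two populations would probably differ, not by how much the result would change.

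Two stronger readings may tempt a reader. One is that the trial lacks a control arm; 4.4, 15.3.2, 15.3.5 and 15.7 rule that out. The other is that the evaluable-only rule causes a known bias or loss of power. The documents give no SD for the % increase in ALC and nothing on how non-evaluable patients would differ from the others, so no size can be stated.

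**What to change.** Rewrite 15.5 as follows.

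- (a) Safety set: all patients who received any dose of rhIL-7-hyFc or placebo, by treatment received.
- (b) Phase II primary ALC set: randomized patients of both arms who received at least one dose of rhIL-7-hyFc or placebo and have a valid ALC at baseline and at about week 4 before adjuvant TMZ. Analyse by assigned arm and label the set modified ITT (evaluable). The dosing condition agrees with 15.3.2, which times evaluability from the first dose.
- (c) PFS set: for phase I and the expansion cohort, patients with at least one dose of rhIL-7-hyFc; for randomized phase II, patients of both arms with at least one dose of rhIL-7-hyFc or placebo, by assigned arm. Phase I is named because 2.3 monitors PFS there. A dose is required because 13.4.6 counts PFS from the start of treatment; if that means study treatment, undosed patients would have no starting point.
- (d) Report by arm how many randomized patients were non-evaluable or replaced, and why.

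The cost is wording in 15.5 and one disposition table by arm. Sample size, visits and tests stay as they are. The change should be made before the phase II ALC data are analysed by arm.

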## **15.6 Early stopping rules**

The study will stop if the following stopping rules are met:

In phase I part of the study, if  $\geq 2$  patients are observed with DLTs out of 6 patients at dose level 1 (60 mcg/kg), the trial will halt.

There is no efficacy stopping rule for the randomized phase II cohort or expansion cohort. The toxicity data for the expansion cohort will be reviewed regularly by the study team and the DSMB. If serious unexpected toxicities occur, the expansion cohort can be stopped early due to safety concern as recommended by the DSMB.

## **15.7 Ad hoc proof-of-concept check**

In the randomized phase II portion of the study, when the number of patients enrolled into each arm is 5 (half of N per arm), we will perform one-time ad-hoc proof-of-concept check on the primary endpoint, the primary % ALC change at  $\sim$ wk4 prior to adjuvant TMZ relative to baseline. If the ad-hoc check finds that the mean % ALC increase evaluated in the rhIL-7-hyFc treated patients is lower than that of placebo treated patients, the study will halt to be reviewed by the PI and DSMB.

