### **15.3.3 Sample size calculation**

We summarized the ALC of all comers seen in our center at 1 month after completion of RT + TMZ and estimated a mean of ALC at 850 and a standard deviation (SD) of 480. This also agrees with data in published literatures (Mendez 2016). We assume that patients on the placebo arm (who usually have received radiation and TMZ post-operative) have the same mean of 850 and SD of 480. Based on 1-sided two sample t-test with equal variance at a 5% level, 8 patients per arm provides 80% power to test a mean ALC of 1486 in the treated patients in comparison to a mean of 850 in the placebo arm. Assuming ~10% dropout rate, we will enroll a total of 20 patients, 10 per arm.

For the whole study spanning through the Phase I and the Phase II study, approximately a minimum of 26 to a maximum of 46 evaluable patients will be enrolled.

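### The mid-trial ALC check in Section 15.7 brings the PI into review of a between-arm comparison in a double-blind phase, and it counts enrolled rather than evaluable patients

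*Combined protocol and SAP*

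**What the plan says.** **Blinding.** Section 4.4 describes the randomized phase II as double-blind: "participant, and physician/study coordinator are all blinded; pharmacist and study statistician are not blinded". It adds: "Only the pharmacist and statistician will know the treatment corresponding to each assignment". The PI is not named as an exception there or elsewhere.

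**The check.** Section 15.7 plans a single look at the primary endpoint, % ALC change at about week 4 before adjuvant TMZ. Its timing is "when the number of patients enrolled into each arm is 5 (half of N per arm"). Its criterion is that "the mean % ALC increase evaluated in the rhIL-7-hyFc treated patients is lower than that of placebo treated patients". If that is met, "the study will halt to be reviewed by the PI and DSMB". The section does not say who prepares the comparison, what the PI receives, or what follows the review.

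**Evaluability.** Section 15.3.2 counts a patient as evaluable only if he or she "completes CBC at baseline and at ~4 weeks after the first dose of NT-17 or placebo" with valid ALC values. It also provides that "Enrolled patients who are not evaluable for the primary endpoint will be replaced so as to meet the study power requirements". The plan therefore treats enrolled and evaluable as different counts.

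**Design figures.** Section 15.3.3: "Based on 1-sided two sample t-test with equal variance at a 5% level, 8 patients per arm provides 80% power", for mean ALC 1486 against 850 with SD 480. No operating characteristics are given for the check.

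**The concern.** Two features of Section 15.7 do not fit the rest of the plan.

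First, a halted between-arm comparison is reviewed by the PI, although Section 4.4 confines knowledge of assignments to two other roles. The PI makes judgements that such knowledge could influence. Section 12 has the PI monitor serious toxicities on an ongoing basis. Section 13.4.2 allows the PI to confirm progression of non-target lesions. PFS is a secondary phase II endpoint (Section 15.3.2) and is compared between arms (Section 15.3.5). A PI who has seen arm-level data halfway through a 20-patient trial could carry it into adverse-event attribution, progression calls and decisions about whom to enrol.

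Second, the trigger is enrolment. When the fifth patient in an arm is enrolled, that patient cannot have a week-4 ALC. Either the check runs on fewer than 5 per arm, or staff wait for the data; the text does not say which.

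**Working it through.** **1. The plan's own figure.** Inputs from Section 15.3.3: difference 1486 - 850 = 636, SD 480, 8 per arm, one-sided 5% t-test. The noncentrality is 636 / (480 × sqrt(2/8)) = 2.65 on 14 degrees of freedom, which gives power 0.809. The stated 80% reproduces.

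**2. How many patients would have data.** Section 15.3.4 expects 1-2 patients per month. Screening may precede the first dose by up to 2 weeks (Section 10.1), so a patient needs about 4 to 6 weeks from randomization to reach a week-4 value. At 1 per month for 4 weeks about 1 patient is pending; at 2 per month for 6 weeks about 3 are. Of 10 enrolled, 7 to 9 have data, or roughly 4 per arm.

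**3. False-halt chance at the planned effect, raw ALC.** With n evaluable per arm, P(halt) = Φ(-636 / (480 × sqrt(2/n))).

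- n = 5: Φ(-636 / 303.6) = Φ(-2.095) = 1.8%
- n = 4: Φ(-636 / 339.4) = Φ(-1.874) = 3.0%

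**4. The same on % change, the scale Section 15.7 uses.** The documents give no SD for % change, no correlation between baseline and week 4, and no distribution. I assumed:

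- lognormal ALC at both times with mean 850 and SD 480, so log-scale variance ln(1 + (480/850)²) = 0.277;
- correlation 0.3 to 0.7 on the log scale;
- baseline of at least 600, from inclusion criterion 5 in Section 3.1;
- the planned effect as multiplication of week-4 ALC by 1486/850 = 1.75.

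Simulated false-halt chances (the low end is correlation 0.7, the high end 0.3):

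| Evaluable per arm | P(halt) at the planned effect |
|---|---|
| 5 | about 1-6% |
| 4 | about 2-9% |

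Without the baseline restriction the ranges are wider: 1.8-9.2% with 5 and 2.9-11.5% with 4. The restriction removes the small denominators that inflate % change, and it belongs in the calculation because it is an entry criterion for this phase.

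**5. Effect on the final test.** Suppose every halt were permanent, on raw ALC with 5 evaluable per arm at the check. In simulation with 10 per arm, power falls from 0.887 to 0.883 and type I error moves from 0.0498 to 0.0490. The check does no material harm to the primary test.

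**6. Blinding.** No arithmetic applies. Section 4.4 gives a closed list of two roles that know assignments. Section 15.7 assigns review of a between-arm result to a third role and sets no limit on its content.

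**The case against.** The strongest reply is that little is exposed.

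- Section 15.7 does not say that tables go to the PI and gives the PI no decision right. A reader might infer that comparative results are routinely sent to the PI; the text does not support that. PI review arises only if the halt triggers, which is unlikely at the planned effect. Section 4.4 also does not name the PI, so that the PI should be blinded is an inference, though a strong one. What stands is that a joint review with the DSMB has little to consider except arm-level data, and nothing restricts it.
- The primary endpoint is a laboratory count that an informed PI can hardly bias. Routine CBCs are not masked and may be drawn locally (Section 10.1, footnote 8), so a rise of the planned size is already partly visible. This stands, and it confines the concern to adverse-event attribution, progression calls and enrolment.
- The proposed recommendation still tells the PI the direction of the difference. That is true; it withholds the size and the individual data.
- A sensible team would read Section 15.7 as meaning patients with week-4 data. That is probably the intention, and saying so costs nothing.

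Two stronger readings should be set aside. A reader might note that with no drug effect and equal numbers the check halts half the time, and call the rule faulty. A futility-type look that halts for review is meant to flag an ineffective drug, the halt is not termination, type I error does not rise, and the fix leaves that probability unchanged. A reader might also suppose that the check would rest on only 3 per arm. That needs 4 of 10 patients without data, more than the accrual rate in Section 15.3.4 suggests.

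**Conclusion.** The point holds as a minor one. Sections 4.4 and 15.7 are not reconciled on whether the PI may see a between-arm result, and if the halt triggers the PI could be unblinded at arm level mid-trial. The consequence is for judgement-based outcomes and enrolment, not materially for the ALC endpoint.

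The trigger wording is a smaller matter. Read literally it gives about 4 rather than 5 evaluable patients per arm, and the false-halt chance at the planned effect rises from 1.8% to 3.0% on raw ALC. On % change it rises from about 1-6% to about 2-9%; those ranges depend on the assumed lognormal shape, correlation and baseline cut-off. The raw-scale figures use the plan's SD of 480, which is stated for absolute ALC.

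**What to change.** Amend Section 15.7 in two sentences:

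1. Run the check once 5 patients in each arm have a valid baseline ALC and a valid week-4 ALC taken before adjuvant TMZ.
2. The statistician, who is already unblinded, reports arm-level results to the DSMB only; the PI receives only a continue or halt recommendation.

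The cost is the wording and a delay of about four weeks to the check. Sample size, endpoint and patient care do not change. The recommendation will still reveal the direction of the difference, and the text can acknowledge this. Label: cheap improvement.
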